4.1 Effectiveness Endpoints

Primary Effectiveness Endpoint

The primary endpoint is binocular High Contrast/High Illumination (HC/HI) VA at distance (4 m or 3 m) at Day 30. This VA is collected with study lenses, on the logMAR scale.

4.2 Effectiveness Hypotheses

[figure not shown]
Primary Effectiveness

The null and alternative hypotheses are formulated in terms of the predefined margin of 0.05 for noninferiority:

$$H_0: \mu_{(T)} - \mu_{(C)} \geq 0.05$$

$$H_a: \mu_{(T)} - \mu_{(C)} < 0.05$$

where $\mu_{(T)}$ and $\mu_{(C)}$ denote the mean distance binocular HC/HI VA at Day 30 for [REDACTED] MF and AOHG MF, respectively, on the logMAR scale.

[figure not shown]
[figure not shown]

4.3 Statistical Methods for Effectiveness Analyses

4.3.1 Primary Effectiveness Analysis

A mixed effects repeated measures model will be utilized to test these hypotheses. The model will include terms for lens, visit, lens by visit interaction, period, sequence, and habitual lens stratum. Within-subject correlation due to the crossover design will also be accounted for in

the model. Lens difference (████ MF minus AOHG MF) and the corresponding one-sided 95% upper confidence limit will be computed at Day 30. Noninferiority in distance VA will be declared if upper confidence limit is less than 0.05.

5 SAFETY ANALYSIS STRATEGY

5.1 Safety Endpoints

The safety endpoints are

- AE
- Biomicroscopy Findings/Slit Lamp Examinations
 - Limbal hyperemia

- Bulbar hyperemia
- Corneal staining
- Conjunctival staining
- Palpebral conjunctival observations
- Corneal epithelial edema
- Corneal stromal edema
- Corneal vascularization
- Conjunctival compression/indention
- Chemosis
- Corneal infiltrates
- Other findings
- Device deficiencies

5.2 Safety Hypotheses

There are no formal safety hypotheses in this study. The focus of the safety analysis will be a comprehensive descriptive assessment of safety endpoints listed in Section 5.1.

5.3 Statistical Methods for Safety Analyses

The analysis set for all safety analyses is defined in Section 2.1. Baseline will be defined as the last measurement prior to exposure to study lenses. For biomicroscopy data, baseline will be defined as Visit 2. Safety variables will be summarized descriptively.

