Habitual lens information (brand, power, lens solution*)	X						
VA with habitual correction (OD, OS, Snellen distance)*	X				X	(X)	х
Keratometry (OD, OS)*	X						
Manifest refraction*	X	(X)	(X)	(X)	(X)	(X)	(X)
BCVA (OD, OS, Snellen distance and near with manifest refraction)*	X	(X)	(X)	(X)	(X)	(X)	(X)
Biomicroscopy	X	X	X		X	X	X

		LENS 1 (Period 1)		LENS 2 (Period 2)			
	Visit 1 Screening / Baseline / Lens Fit	Visit 2 Dispense Lens 1	Visit 3 Day 30 Follow-up Lens 1	Visit 3 Dispense Lens 2	Visit 4 Day 30 Follow-up Lens 2 / Exit	Unscheduled Visit	Early Exit
Procedure/ Assessment		Day 1 [3-5 days after Visit 1	Day 30 (- 2/+1) Days	Day 1 [same day as Lens 1 Day 30 Follow-up visit]	Day 30 (- 2/+1) Days	N/A	N/A
						Optional with Unplanned Lens Replacement only	
Inclusion/Exclusion criteria	X						
Randomize	X						
Study lens parameters optimization and fitting per randomization scheme (Test and Comparator)*	Х						

		LENS 1 (Period 1)		LENS 2 (Period 2)			
	Visit 1 Screening / Baseline / Lens Fit	Visit 2 Dispense Lens 1	Visit 3 Day 30 Follow-up Lens 1	Visit 3 Dispense Lens 2	Visit 4 Day 30 Follow-up Lens 2 / Exit	Unscheduled Visit	Early Exit
Procedure/ Assessment		Day 1 [3-5 days after Visit 1	Day 30 (- 2/+1) Days	Day 1 [same day as Lens 1 Day 30 Follow-up visit]	Day 30 (- 2/+1) Days	N/A	N/A
Study lens power to be dispensed	X						
Dispense study lenses per randomization scheme		X		X		(X)	
		•	•	•	•	-	•
LogMAR HC/HI VA at: • Distance (4 m or 3 m; OU)		X	X	X	X	(X)	X

		LENS 1 (Period 1)		LENS 2 (Period 2)			
	Visit 1 Screening / Baseline / Lens Fit	Visit 2 Dispense Lens 1	Visit 3 Day 30 Follow-up Lens 1	Visit 3 Dispense Lens 2	Visit 4 Day 30 Follow-up Lens 2 / Exit	Unscheduled Visit	Early Exit
Procedure/ Assessment		Day 1 [3-5 days after Visit 1	Day 30 (- 2/+1) Days	Day 1 [same day as Lens 1 Day 30 Follow-up visit]	Day 30 (- 2/+1) Days	N/A	N/A
							•
			•		•		

Page 25 of 67

		LENS 1 (Period 1)		LENS 2 (Period 2)			
	Visit 1 Screening / Baseline / Lens Fit	Visit 2 Dispense Lens 1	Visit 3 Day 30 Follow-up Lens 1	Visit 3 Dispense Lens 2	Visit 4 Day 30 Follow-up Lens 2 / Exit	Unscheduled Visit	Early Exit
Procedure/ Assessment		Day 1 [3-5 days after Visit 1	Day 30 (- 2/+1) Days	Day 1 [same day as Lens 1 Day 30 Follow-up visit]	Day 30 (- 2/+1) Days	N/A	N/A
Adverse Events	X	X	X	X	X	X	X
Device deficiencies	X	X	X	X	X	X	X
Exit Form	(X)	(X)	(X)	(X)	X		X

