8.1 Inclusion Criteria

Written informed consent must be obtained before any study specific assessment is performed. Upon signing informed consent, the subject is considered enrolled in the study.

Subjects eligible for inclusion in this study must fulfill **all** of the following criteria:

- 1. Subject must be able to understand and sign an IRB/IEC approved Informed Consent form.
- 2. Willing and able to attend all scheduled study visits as required per protocol.
- 3. Subject must be at least 40 years of age.
- 4. Subject must be willing to stop wearing their habitual contact lenses and be willing to not wear glasses during study lens wear for the duration of study participation.

- 5. Current wearer of daily disposable and biweekly/monthly replacement multifocal soft contact lenses (including AOHG MF) in both eyes for a minimum of 5 days per week and 8 hours per day during the past 3 months.
- 6. Manifest cylinder ≤ 0.75 D in each eye.
- 7. BCVA distance (as determined by manifest refraction at screening) 20/25 or better in each eye with a spherical refractive error between -1.00 and 4.00 D, and requiring a near ADD of LO, MED or HI (ADD of +0.75 D to +2.50 D) in each eye.

Note: Study lens parameters available in this study are:

- LO ADD with -1.25 D to -4.00 D (in 0.25 D steps)
- MED ADD with -1.00 D to -4.00D (in 0.25 D steps)
- HI ADD with -1.50 D to -3.00 D (in 0.25 D steps)
- 8. Subject willing to wear the study contact lenses as defined for the full duration of the study.
- 9. Subject must possess spectacles and be willing to wear habitual spectacles for vision correction when study lenses are not worn, during wash out period and as directed by PI.

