8.2 Exclusion Criteria

Subjects fulfilling any of the following criteria are not eligible for participation in this study.

- 1. Any anterior segment infection, inflammation, or abnormality or disease (including systemic) that contraindicates contact lens wear, as determined by the Investigator.
- 2. Any use of systemic or ocular medications for which contact lens wear could be contraindicated, as determined by the Investigator.
- 3. History of refractive surgery or planning to have refractive surgery during the study, or irregular cornea in either eye.
- 4. Ocular or intraocular surgery (excluding placement of punctal plugs) within the previous 12 months or planned during the study.
- 5. Biomicroscopy findings at screening that are moderate (Grade 3) or higher and/or corneal vascularization that is mild (Grade 2) or higher, and/or any infiltrate.

- 6. Current or history of pathologically dry eye in either eye that, in the opinion of the Investigator, would preclude contact lens wear.
- 7. Current or history of herpetic keratitis in either eye.
- 8. Eye injury in either eye within 12 weeks immediately prior to enrollment for this trial.
- 9. Current or history of intolerance, hypersensitivity, or allergy to any component of the study products.
- 10. Currently pregnant or lactating, as stated by subject.
- 11. Any history of amblyopia, strabismus or binocular vision abnormalities.
- 12. Any use of topical ocular medications and artificial tear or rewetting drops that would require instillation during contact lens wear.
- 13. The Investigator, his/her staff, family members of the Investigator, family members of the Investigator's staff, or individuals living in the households of the aforementioned persons may not participate in the study.
- 14. Participation of the subject in a clinical trial within the previous 30 days or currently enrolled in any clinical trial.
- 15. Monovision contact lens wearers and wearers of contact lens in one eye only.
- 16. Wearing habitual contact lenses in an extended wear modality (routinely sleeping in lenses for at least 1 night per week) over the last 3 months prior to enrollment.

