12.6 Safety Analyses

The safety endpoints are:

- AEs
- Biomicroscopy findings
- Device Deficiencies

There are no safety hypotheses planned in this study. The focus of the safety analysis will be a comprehensive descriptive assessment of occurrence of adverse events as well as the other listed parameters.

All AEs occurring from the time a subject signs informed consent to study exit will be accounted for in the reporting. Safety analyses will be conducted using the safety analysis set on a treatment-emergent basis. Descriptive summaries (frequencies and percentages) for ocular and nonocular AEs will be presented by Medical Dictionary for Regulatory Activities Preferred Terms. AEs leading to study discontinuation and SAEs will be identified. Individual subject listings will be provided, as necessary.

Individual subject listings will be provided for AEs that occur after signing informed consent but prior to exposure to IP.

Each biomicroscopy parameter will be tabulated by its grade. For each biomicroscopy parameter, counts and percentages of eyes that experience an increase of ≥ 2 grades from baseline (last assessment prior to study lens exposure) to any subsequent visit within the same period will be presented. A supportive listing will be generated which will include all biomicroscopy data from all visits within the same period for those eyes experiencing the increase.

[figure not shown]
Two listings for device deficiencies, prior to exposure to study contact lenses and treatmentemergent, will be provided. Additionally, each device deficiency category will be tabulated.

No inferential testing will be conducted for the safety analyses.

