1.2 Study Description

Key components of the study are summarized in Table 1-1.

[figure not shown]
Table 1-1 **Study Description Summary**

Study Design	Prospective, randomized, [REDACTED] bilateral, crossover, double-masked
Study Population	The subject population consists of volunteer subjects aged \geq 40 years, who are habitual daily disposable and biweekly/monthly replacement soft multifocal contact lens wearers for at least past 3 months and wear their habitual lenses at least 5 days per week and at least 8 hours per day. Target to complete: 84 Planned to enroll: ~96
Number of Sites	~8 US
Test Product	[REDACTED] Multifocal contact lenses ([REDACTED] MF; lehfilcon A; LID210464)
Comparator Product	AIR OPTIX [®] plus HydraGlyde [®] Multifocal contact lenses (AOHG MF; lotrafilcon B)

Planned Duration of Exposure	~60 days total duration (test and comparator): Test Product: 30 (-2/+1) days Comparator Product: 30 (-2/+1) days
Visits	Visit 1: Screening/Baseline/Lens Fit Visit 2: Dispense Lens 1 [3-5 days after Visit 1] Visit 3: Day 30 Follow-up Lens 1/Dispense Lens 2 [Day 30 (-2/+1)] Visit 4: Day 30 Follow-up Lens 2/Exit [Day 30 (-2/+1)] [REDACTED] [REDACTED]

A study design schematic is depicted in Figure 1-1.

Figure 1-1 Study Design

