2 ANALYSIS SETS

2.1 Safety Analysis Set

Safety analyses will be conducted using the safety analysis set on a treatment-emergent basis. As such, the safety analysis set will include all subjects/eyes exposed to any study lenses evaluated in this study. [REDACTED]

any adverse event (AE) or device deficiency occurring after Informed Consent and prior to the initial exposure to the study lenses (test or comparator) under evaluation in this clinical protocol will be listed as pre-treatment.

For treatment-emergent safety analyses, subjects/eyes will be categorized under the actual study lenses exposed in the corresponding lens sequence.

Adverse events occurring from the time of informed consent but prior to first exposure to study lenses will be summarized in subject listings.

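### SAP 5.3 sets the biomicroscopy baseline at Visit 2 and names none for Period 2, so the Lens 2 count of ≥2-grade increases measures net change since before Lens 1

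*SAP*

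**What the plan says.** SAP 5.3 first defines the safety baseline in general terms, as the last value before study lenses are worn. It then fixes one visit: "For biomicroscopy data, baseline will be defined as Visit 2". Neither 5.3 nor 5.3.2, which lists the ≥2-grade table and listing, gives a rule for the second period. No redaction is marked in either section.

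Protocol 12.6 counts eyes with an "increase of ≥ 2 grades from baseline (last assessment prior to study lens exposure) to any subsequent visit within the same period". Its supportive listing is to "include all biomicroscopy data from all visits within the same period for those eyes experiencing the increase".

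Both documents attribute safety data by lens; in SAP 2.1, "subjects/eyes will be categorized under the actual study lenses exposed in the corresponding lens sequence". Protocol Table 3-1 heads the Lens 2 dispensing column "Day 1 [same day as Lens 1 Day 30 Follow-up visit". Biomicroscopy is scheduled at Visits 1, 2, 3 and 4. At Visit 3 it is marked in the Lens 1 follow-up column and left blank in the Lens 2 dispensing column. An exam between the two lenses therefore exists, but neither document names it as a baseline.

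**The concern.** A by-lens table should show what happened while that lens was worn. For Lens 1, Visit 3 against Visit 2 does this. For Lens 2, a Visit 2 baseline makes the scheduled comparison Visit 4 against an exam made before either lens was dispensed, so whatever happened on Lens 1 is included.

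Biomicroscopy is one of three named safety endpoints, and the safety objective is to describe the profile of each product. The risk is a Lens 2 count that includes findings that began on Lens 1 and leaves out some that began on Lens 2. The programmer would also have to choose the Period 2 baseline without written guidance.

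**Working it through.** The plan states no figure on this point, so there is none to reproduce. The check is an identity, an enumeration and an illustration.

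**Identity.** With V2, V3 and V4 the grades at Visits 2, 3 and 4: V4 − V2 = (V3 − V2) + (V4 − V3). Only the last term is change on Lens 2.

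| V2-V3-V4 | Lens 1 (V3 − V2) | Lens 2 against Visit 2 | Lens 2 against Visit 3 |
|---|---|---|---|
| 0-2-2 | +2, counted | +2, counted | 0, not counted |
| 0-3-2 | +3, counted | +2, counted | −1, not counted |
| 0-1-2 | +1, not counted | +2, counted | +1, not counted |
| 2-0-2 | −2, not counted | 0, not counted | +2, counted |

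**Enumeration.** Assumptions: grades run 0-4 (the scale is in the Manual of Procedures, which is not supplied); scheduled exams only; the screening limits of Protocol 8.2 still hold at Visit 2, so V2 is 0-2. This gives 3 × 5 × 5 = 75 patterns. These are patterns, not probabilities.

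- Counted under Lens 2 against Visit 2: 15 (V2 = 0) + 10 (V2 = 1) + 5 (V2 = 2) = 30.
- Counted against Visit 3: 6 (V3, V4) pairs × 3 = 18.
- Counted by both: 14. Visit 2 only: 30 − 14 = 16. Visit 3 only: 18 − 14 = 4 (1-0-2, 2-0-2, 2-0-3, 2-1-3).
- Classification changes in 16 + 4 = 20 of 75. Of the 16, 13 are also counted under Lens 1, four of them after improving on Lens 2 (0-3-2, 0-4-2, 0-4-3, 1-4-3). Three are stepwise rises (0-1-2, 1-2-3, 2-3-4).

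For corneal vascularization, subjects are excluded at screening for "corneal vascularization that is mild (Grade 2) or higher", so V2 is 0-1 and there are 2 × 5 × 5 = 50 patterns. Against Visit 2, 25 count; against Visit 3, 12; by both, 11. Classification changes in 14 + 1 = 15.

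**Overlap with mandatory AE reporting.** Protocol 11.1 requires a report at corneal staining grade 3 or higher and neovascularization grade 2 or higher (taken here as the vascularization parameter).

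- Staining: 16 of the 20 affected patterns reach grade 3 at Visit 3 or 4. Four do not: 0-1-2, 0-2-2, 1-0-2 and 2-0-2.
- Vascularization: all 15 affected patterns reach grade 2.

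**Illustration of carry-over.** The documents give no event rate p and no persistence r to Visit 4, so both are assumed. The 84 planned completers give 168 eyes per lens. Half of these, 84, wear that lens second. Extra eyes counted under each lens = 84 × p × r.

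| p | r = 25% | r = 50% | r = 75% |
|---|---|---|---|
| 1% | 0.21 | 0.42 | 0.63 |
| 3% | 0.63 | 1.26 | 1.89 |
| 5% | 1.05 | 2.10 | 3.15 |

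With the same p on both lenses and 1:1 sequences, each lens gains the same expected number. With rates pA and pB, the difference in counts narrows by 84 × r × (pA − pB). At 5% against 1% and r = 75%, this is 84 × 0.75 × 0.04 = 2.52 eyes. The illustration covers carry-over only, not stepwise or missed rises.

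**The case against.** A reader might infer that SAP 5.3 and Protocol 12.6 contradict each other. The documents do not establish that. Their general definitions of baseline agree. In Protocol 12.6 the same-period phrase grammatically limits the follow-up visits, not the baseline. Study lenses are fitted at Visit 1, so the SAP may name Visit 2 only to settle which pre-dispensing exam counts. Nor does the Protocol clearly make Visit 3 the Period 2 baseline, since that exam sits in the Lens 1 column. What remains is a gap: Visit 2 lies in Period 1, and neither text names a baseline for Lens 2.

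A reader might also infer that the table favours one lens. With equal rates and 1:1 sequences no between-lens bias is expected, and with unequal rates the difference shrinks. This balance does not stop an eye being counted under the wrong lens.

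It is fair to say that an exam before either lens is a defensible descriptive baseline, because Visit 3 follows 30 days on Lens 1. That supports showing cumulative change, but not labelling it as change on Lens 2.

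Other outputs also help. SAP 5.3.2 tabulates grades by visit, and SAP 5.3.1 assigns AEs to a lens by onset. These cover only part of the gap. The by-visit table does not link one eye's Visit 3 and Visit 4 grades, and for findings outside the mandatory list AE reporting rests largely on the investigator's judgement of clinical relevance (Protocol 11.2).

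**Conclusion.** The point holds as a minor one. Read literally, SAP 5.3 is a stated rule that yields a wrong by-lens count for Lens 2, and not merely a missing detail. The arithmetic of that consequence needs no assumption. The pattern counts rest on the assumed 0-4 scale and on the screening limits holding at Visit 2. The estimate of about 0 to 3 of 168 eyes per lens rests wholly on assumed rates and persistence, so the real size cannot be derived from the documents.

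The table is descriptive, SAP 5.2 plans no safety hypothesis, and the primary noninferiority analysis does not use these data. SAP 5.3 and Protocol 12.6 should be called unreconciled, not contradictory.

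**What to change.** In SAP 5.3, for the ≥2-grade table and listing:

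- Use Visit 2 as baseline for Period 1, and the Visit 3 exam made before Lens 2 is dispensed as baseline for Period 2. Make this the main by-lens count.
- Keep change from Visit 2 as a second column, labelled cumulative.
- Print the Visit 2 and Visit 3 grades in the Lens 2 listing.
- Align the baseline wording of SAP 5.3 and Protocol 12.6, before unmasking, so that the choice is not made after the fact.

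The cost is one derived variable, one table column and some wording; the exam is already scheduled. Protocol 12 allows a change to the analysis plan by amendment or by a statement in the clinical study report. The downside is that a Visit 3 baseline alone would not count 0-2-2 under Lens 2, nor 0-1-2 under either lens, which is why the Visit 2 column stays.

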5.3.1 Adverse Events

The applicable definition of an AE is in the study protocol. All AEs occurring from when a subject signs informed consent to the time of their study exit will be accounted for in the reporting.

Pre-treatment AEs will be separated from treatment-emergent AEs occurring during the study period. A pre-treatment AE is an event that occurs after signing informed consent but prior to exposure to study lenses. The period for treatment-emergent AE analysis starts from exposure to study lenses until the subject completes or is discontinued from the study. Each AE will be summarized under the exposed lens based upon the event onset date/time, up until the start of the next lens in the crossover sequence.

The following tables and supportive listings will be provided:

- Incidence of All Ocular Treatment-Emergent Adverse Events

- Incidence of Ocular Serious Treatment-Emergent Adverse Events
- Incidence of Ocular Significant Nonserious Treatment-Emergent Adverse Events
- Incidence of All Nonocular Treatment-Emergent Adverse Events
- Incidence of Nonocular Serious Treatment-Emergent Adverse Events
- Listing of All Ocular Treatment-Emergent Adverse Events
- Listing of All Nonocular Treatment-Emergent Adverse Events
- Listing of All Ocular Pre-Treatment Adverse Events
- Listing of All Nonocular Pre-Treatment Adverse Events

5.3.2 Biomicroscopy Findings/Slit Lamp Examination

The following tables and supportive listings will be provided:

- Frequency and Percentage for Biomicroscopy Findings by Visit
- Incidence of Increased Severity by 2 or More Grades in Biomicroscopy Findings
- Listing of Subjects with Other Biomicroscopy Findings
- Listing of Subjects with Conjunctival Compression/Indentation or Chemosis
- Listing of Subjects with Increased Severity by 2 or More Grades in Biomicroscopy Findings
- Listing of Subjects with Infiltrates

5.3.3 Device Deficiencies

The following tables and supportive listings will be provided:

- Frequency of Treatment-Emergent Device Deficiencies
- Listing of Treatment-Emergent Device Deficiencies
- Listing of Device Deficiencies Prior To Treatment Exposure

7 SAMPLE SIZE AND POWER CALCULATIONS

Sample size required for [REDACTED] the primary effectiveness [REDACTED]
[REDACTED], at 90% power and one-sided $\alpha=0.05$, is summarized below:

Endpoint	SD (Paired Difference)	N/Sequence (NI margin = 0.05)
Distance VA	0.0845	13/Sequence
[REDACTED]	[REDACTED]	[REDACTED]
[REDACTED]	[REDACTED]	[REDACTED]nce

10 APPENDIX

[figure not shown]
[figure not shown]
[figure not shown]
[figure not shown]
Table 10-1 Schedule of Study Procedures and Assessments

Procedure/ Assessment	Visit 1 Screening / Baseline / Lens Fit	LENS 1 (Period 1)		LENS 2 (Period 2)		Unscheduled Visit	Early Exit
		Visit 2 Dispense Lens 1	Visit 3 Day 30 Follow-up Lens 1	Visit 3 Dispense Lens 2	Visit 4 Day 30 Follow-up Lens 2 / Exit		
Procedure/ Assessment		Day 1 [3-5 days after Visit 1] 	Day 30 (- 2/+1) Days 	Day 1 [same day as Lens 1 Day 30 Follow-up visit] 	Day 30 (- 2/+1) Days 	N/A	N/A
Informed Consent	X						
Demographics	X						
Medical History ^o	X	X	X		X	X	X
Concomitant Medications ^o	X	X	X		X	X	X
Habitual lens information (brand, power, lens solution*)	X						
VA with habitual correction (OD, OS, Snellen distance)*	X				X	(X)	X
Keratometry (OD, OS)*	X						

		LENS 1 (Period 1)		LENS 2 (Period 2)		Unscheduled Visit	Early Exit
		Visit 1 Screening / Baseline / Lens Fit	Visit 2 Dispense Lens 1	Visit 3 Day 30 Follow-up Lens 1	Visit 3 Dispense Lens 2		
Procedure/ Assessment			Day 1 [3-5 days after Visit 1] [REDACTED] [REDACTED] [REDACTED] [REDACTED]	Day 30 (- 2/+1) Days	Day 1 [same day as Lens 1 Day 30 Follow-up visit]	Day 30 (- 2/+1) Days	N/A
Manifest refraction*	X	(X)	(X)	(X)	(X)	(X)	(X)
BCVA (OD, OS, Snellen distance with manifest refraction)*	X	(X)	(X)	(X)	(X)	(X)	(X)
Biomicroscopy	X	X	X		X	X Optional with Unplanned Lens Replacement only	X
	[REDACTED] [REDACTED]	■	■	■	■	■	■
Inclusion/Exclusion criteria	X						
Randomize	X						
Study lens parameters optimization and fitting per randomization scheme (Test and Comparator)*	X						
	[REDACTED]	■					

		LENS 1 (Period 1)		LENS 2 (Period 2)		Unscheduled Visit	Early Exit
		Visit 1 Screening / Baseline / Lens Fit	Visit 2 Dispense Lens 1	Visit 3 Day 30 Follow-up Lens 1	Visit 3 Dispense Lens 2		
Procedure/ Assessment			Day 1 [3-5 days after Visit 1] [REDACTED] [REDACTED] [REDACTED] [REDACTED]	Day 30 (- 2/+1) Days	Day 1 [same day as Lens 1 Day 30 Follow-up visit]	Day 30 (- 2/+1) Days	N/A
Study lens power to be dispensed	[REDACTED]	X					
Dispense study lenses per randomization scheme	[REDACTED]	■					
	[REDACTED]						
	[REDACTED]		■	■	■	■	■
	[REDACTED]						
	[REDACTED]						
	[REDACTED]						
LogMAR HC/HI VA at: • Distance (4 m or 3 m; [REDACTED] OU)	[REDACTED]		X	X	X	X	X

		LENS 1 (Period 1)		LENS 2 (Period 2)		Unscheduled Visit	Early Exit
		Visit 1 Screening / Baseline / Lens Fit	Visit 2 Dispense Lens 1	Visit 3 Day 30 Follow-up Lens 1	Visit 3 Dispense Lens 2		
Procedure/ Assessment			Day 1 [3-5 days after Visit 1] 	Day 30 (- 2/+1) Days 	Day 1 [same day as Lens 1 Day 30 Follow-up visit] 	Day 30 (- 2/+1) Days 	N/A 
							
							
							
							
							
							
							
							
							
							
							
							
							
							
							
							
							
							
							
							
							
							
							
							
							
				<img alt="Timeline diagram showing a single horizontal bar." data-bbox="525			

		LENS 1 (Period 1)		LENS 2 (Period 2)		Unscheduled Visit	Early Exit
		Visit 1 Screening / Baseline / Lens Fit	Visit 2 Dispense Lens 1	Visit 3 Day 30 Follow-up Lens 1	Visit 3 Dispense Lens 2		
Procedure/ Assessment			Day 1 [3-5 days after Visit 1] 	Day 30 (- 2/+1) Days 	Day 1 [same day as Lens 1 Day 30 Follow-up visit] 	Day 30 (- 2/+1) Days 	N/A 
							
							
							
Adverse Events	X	X	X	X	X	X	X
Device deficiencies	X	X	X	X	X	X	X
Exit Form	(X)	(X)	(X)	(X)	X		X

(X) assessment performed as necessary, e.g., decrease of VA by 2 lines or more with investigational product (IP), for example when comparing between V3 and V2 for Distance VA with Lens 1 and between V4 and V3 for Distance VA with Lens 2.

* Source only (source provided to sponsor upon request).

∞ Concomitant medications (past 30 days) and Medical History (past year) must be fully documented and collected in the subject source documents with targeted collection in EDC.
